9.8.2 Clinical Laboratory Results

Clinical hematology, coagulation panel, biochemistry, and urinalysis data will be summarized at each scheduled assessment. Shifts for clinical laboratory results that can be graded according to CTCAE v5.0 will be summarized by CTCAE grade. Shifts for other numeric laboratory

results will be by high/normal/low flag. Shifts for all other laboratory results will be by normal/abnormal flag.

Summaries by visit will include data from scheduled assessments, and all data will be reported according to the nominal visit date for which it was recorded. Unscheduled data will be included in “worst-case post-Baseline” summaries, which will capture a worst case across all scheduled and unscheduled visits after the first dose of study treatment. Further details will be provided in the SAP.

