I will not disclose information regarding this clinical investigation or publish results of the investigation without authorization from ADC Therapeutics SA.

Signature of Principal Investigator

Date

Printed Name of Principal Investigator

Summary of Changes for Protocol Amendment 3.0

The primary reason for Protocol Amendment 3 is to align the frequency of laboratory evaluations for patients treated with idelalisib with the idelalisib Summary of Product Characteristics (SmPC); to exclude patients with history of hypersensitivity to any of the excipients of study drugs; to align contraception guidance for women of childbearing potential (WOCBP) receiving idelalisib treatment with the idelalisib SmPC; and to extend SAE reporting duration to at least 5 half-lives after the last loncastuximab tesirine dose based on regulatory authority request.

The summary of changes and the rationale in Protocol Amendment 3.0 is as follows:

- Changed treatment cycle length for the idelalisib arm from 3 weeks to 4 weeks and added hematology tests every 2 weeks (Q2W) for the initial 6 months (cycles 1 to 7) and ALT/AST/total bilirubin tests Q2W for the initial 3 months (cycles 1 to 4) of idelalisib treatment.
 - [Section 4.1 Overview & Section 4.2.3 Treatment Period](#): Amended the idelalisib treatment cycle length from 3 weeks to 4 weeks.
 - Schedule of Events: Split Schedule of Events (SoE) table (Table 1) to [Table 1](#) Schedule of Events for Loncastuximab Tesirine Arm and [Table 2](#) Schedule of Events for Idelalisib Arm for a better clarity.
 - Added hematology tests on day 15 for cycles 1 to 7 and AST/ALT /total bilirubin tests on day 15 for cycles 1 to 4 for patients in idelalisib arm in [Table 2](#).
 - PRO-CTCAE questionnaire for patients in the idelalisib arm ends in cycle 7 to correspond to 6-month treatment duration compared to loncastuximab tesirine. Updated the schedule for PRO-CTCAE questionnaire in SoE ([Table 2](#)).
 - [Section 7 Study Assessments and Procedures](#) was revised to reference [Table 1](#) and [Table 2](#) for the study events, where applicable.
- [Section 5.2 Exclusion Criteria](#): Added an exclusion criterion: History of hypersensitivity to any of the excipients of loncastuximab tesirine or idelalisib.

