Abbreviations: ADA: anti-drug antibody; AE: adverse events; BP: blood pressure; β -HCG: β subunit of Human chorionic gonadotropin; C: cycle; C1D1: cycle 1 day 1; [REDACTED] CMV: cytomegalovirus; CT: computerized tomography; ECG: electrocardiogram; ECOG: Eastern Cooperative Oncology Group; EOI: end of infusion; EOT: end of treatment; FACT-Lym: The Functional Assessment of Cancer Treatment-Lymphoma questionnaire; FDG: (18)F-fluorodeoxyglucose; [REDACTED]; HBV: hepatitis B virus; HCV: hepatitis C virus; HIV: human immunodeficiency virus; HR: heart rate; ICF: informed consent form; IV: Intravenous; MRI: Magnetic resonance imaging; PCR: polymerase chain reaction; PK: pharmacokinetics; PRO-CTCAE: Patient-Reported Outcomes Version of the Common Terminology Criteria for Adverse Events; RR: respiratory rate; SAE: serious AEs; Temp: temperature;.

Visit Scheduling Windows:

- Treatment Period: Visit day \pm 3 days (excluding C1D1 which is the reference day).
- EOT: As soon as possible after decision to discontinue the study treatment but preferably at least 30 days after last dose of study treatment unless a new anticancer treatment is planned to be administered before the 30 days, in which case EOT should be conducted before initiation of the new anticancer treatment.
- Follow-up Period: Visit day \pm 14 days.

²Vitals should be taken at pre-dose and EOI for every loncastuximab tesirine dosing visit.

³Positron-emission tomography-computed tomography will be used to perform imaging study. If disease is not FDG-avid at baseline, CT or MRI may be used. Screening imaging must be performed within 4 weeks prior to C1D1 and the same assessment method must be used throughout the study. Week 6 and Week 12 imaging should be performed within \pm 5 days of the scheduled timepoint. All other imaging for disease assessment should be performed within \pm 2 weeks of the

scheduled time point. Imaging for disease assessment should be performed at the scheduled timepoint even if drug dosing is delayed. Additional disease assessments may be obtained, if clinically indicated.

⁴During follow-up period disease assessments to be performed in patients who discontinued study treatment for reasons other than disease progression or initiation of other anti-cancer therapy (except for hematopoietic stem cell transplant).

⁵ \leq 3days prior to administration of study treatment for loncastuximab tesirine arm patients.

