4.2.3 Treatment Period

The treatment period will start on the date when a patient is administered the first dose of study treatment and continues until the end of treatment (EOT) visit (see below).

A treatment cycle is defined as 3 weeks (i.e., 21 days) for patients assigned to loncastuximab tesirine treatment. A treatment cycle is defined as 4 weeks (i.e., 28 days) for patients assigned to idelalisib treatment. Patients will receive either IV loncastuximab tesirine on Day 1 of each cycle, or idelalisib 150 mg BID orally Days 1-28 every cycle. Patients may continue treatment until disease progression, unacceptable toxicity, death, or other discontinuation criteria, whichever occurs first.

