Grade 4 infusion related reaction	
• Permanently discontinue loncastuximab tesirine
Hy's law (AST and/or ALT $> 3 \times \text{ULN}$ and bilirubin $> 2 \times \text{ULN}$)	
• Permanently discontinue loncastuximab tesirine. Hy's law defined as: AST and/or ALT $> 3 \times \text{ULN}$ and bilirubin $> 2 \times \text{ULN}$, and without initial findings of cholestasis (ALP activity $< 2 \times \text{ULN}$) and no other reason that could explain the combination of increased transaminases and serum total bilirubin, such as viral hepatitis A, B, or C, preexisting or acute liver disease, or another drug capable of causing the observed injury

Table 5. Criteria for Dose Delay or Dose Modification of Idelalisib

Toxicity	Idelalisib
Grade ≥ 2 symptomatic pneumonitis of any severity	Permanently discontinue idelalisib
Grade 2 increased ALT/AST/bilirubin or diarrhea	Maintain idelalisib dose. Monitor at least weekly until normal
Grade 3 increased ALT/AST/bilirubin or diarrhea	Withhold idelalisib. Monitor at least weekly until normal, then may resume idelalisib at 100 mg BID.
Grade 4 increased ALT/AST/bilirubin or diarrhea	Discontinue idelalisib permanently
Grade 3 neutropenia and/or thrombocytopenia	Maintain Idelalisib dose. Monitor ANC and/or platelet count at least weekly
Grade 4 neutropenia and/or thrombocytopenia	Withhold idelalisib. Monitor ANC and/or platelet count at least weekly. When neutropenia and thrombocytopenia are Grade 3 or less, may resume idelalisib at 100 mg BID
Grade ≥ 3 sepsis or pneumonia	Withhold idelalisib until infection has resolved.
Active CMV infection of any grade or viremia (positive PCR or antigen test)	Withhold idelalisib until the infection and viremia have resolved. If idelalisib is resumed, monitor by PCR or antigen for CMV reactivation at least monthly.
Suspected PJP infection of any grade.	Withhold idelalisib. Permanently discontinue idelalisib if PJP infection is confirmed.
Other Grade ≥ 3 non-hematologic toxicities	Withhold idelalisib until resolved, then may resume idelalisib at 100 mg BID. If the same grade ≥ 3 toxicity recurs after resuming idelalisib, permanently discontinue idelalisib
Anaphylaxis, Intestinal Perforation, Stevens-Johnson syndrome (SJS) and toxic epidermal necrolysis (TEN)	Permanently discontinue idelalisib

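### Worst-case laboratory summaries ignore sampling schedules that differ by arm and analyte, so side-by-side worst-grade percentages are not comparable, and the direction of bias varies

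*Combined protocol and SAP*

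**What the plan says.** Section 9.8.2 describes by-visit summaries from scheduled assessments, reported by nominal visit. It adds worst-case post-baseline summaries that include unscheduled data, "which will capture a worst case across all scheduled and unscheduled visits after the first dose of study treatment". It states no end to that window and no rule for unequal sampling. It closes with "Further details will be provided in the SAP"; no separate SAP text was available for this review.

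The sampling that feeds the summaries is set elsewhere in the protocol:

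- **Loncastuximab tesirine.** Section 4.2.3: "A treatment cycle is defined as 3 weeks (i.e., 21 days) for patients assigned to loncastuximab tesirine treatment". Table 1 schedules hematology and chemistry on Day 1 of each cycle and at end of treatment (EOT). Its footnote 5 places on-treatment samples at most "3days prior to administration of study treatment for loncastuximab tesirine arm patients".
- **Idelalisib.** Section 4.2.3: "A treatment cycle is defined as 4 weeks (i.e., 28 days) for patients assigned to idelalisib treatment". Table 2 schedules hematology and chemistry on Day 1 and at EOT. The Amendment 3.0 summary records the additional tests, "Added hematology tests on day 15 for cycles 1 to 7 and AST/ALT /total bilirubin tests on day 15 for cycles 1 to 4", and the current Table 2 shows the same. No other chemistry is taken on Day 15.
- **Toxicity-triggered tests.** Table 5 asks for at least weekly tests on idelalisib from Grade 2 ALT, AST or bilirubin. For Grade 3 neutropenia or thrombocytopenia it says "Maintain Idelalisib dose. Monitor ANC and/or platelet count at least weekly". Table 4, for loncastuximab tesirine, gives no monitoring interval.
- **Clinically indicated tests.** Section 7.4.5 allows additional samples in either arm.

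**The concern.** A patient's worst grade is a maximum over that patient's samples. With the same underlying risk, more samples give a higher chance of recording a high grade. If the arms are sampled at different rates, the difference between their worst-grade percentages mixes toxicity with ascertainment.

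Timing adds to this. A scheduled loncastuximab tesirine sample falls about 18 to 21 days after the previous infusion, so a fall that recovers within the cycle can be missed. Idelalisib is taken twice daily, so its Day 15 sample matters for frequency rather than for distance from a dose.

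Laboratory change is a listed secondary safety endpoint, and Sections 2.1 and 9.1 tie the sample size to safety data on about 100 loncastuximab tesirine patients. Section 1.2.3 lists neutropenia, thrombocytopenia, GGT increase and transaminase elevation among the common Grade 3 or higher events of one or both drugs. Worst-grade columns for the two arms are likely to be read side by side.

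**Working it through.** The plan gives no figure for these summaries, so there is nothing to reproduce. The check counts samples and then illustrates the effect under stated assumptions.

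**1. Scheduled sampling weeks after Cycle 1 Day 1** (Tables 1 and 2, Section 4.2.3; no delays, EOT excluded)

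- Loncastuximab tesirine, all analytes: 3, 6, 9, 12 and so on, every 3 weeks.
- Idelalisib hematology: every 2 weeks to week 28 (last Day 15 sample at week 26), then every 4 weeks.
- Idelalisib ALT, AST and total bilirubin: every 2 weeks to week 16 (last Day 15 sample at week 14), then every 4 weeks.
- Idelalisib other chemistry (GGT, ALP, amylase, lipase and the rest): every 4 weeks.

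**2. Cumulative scheduled samples per patient after first dose**

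| To week | Loncastuximab tesirine, any analyte | Idelalisib hematology | Idelalisib ALT/AST/bilirubin | Idelalisib other chemistry |
|---|---|---|---|---|
| 12 | 4 | 6 | 6 | 3 |
| 16 | 5 | 8 | 8 | 4 |
| 24 | 8 | 12 | 10 | 6 |
| 28 | 9 | 14 | 11 | 7 |
| 52 | 17 | 20 | 17 | 13 |
| 104 | 34 | 33 | 30 | 26 |

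Idelalisib leads early for hematology and the three liver tests. Liver-test counts are equal by week 52 and hematology counts nearly equal by week 104. Loncastuximab tesirine leads throughout for other chemistry.

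**3. Effect on a worst-grade percentage.** Assume each sample has the same chance p of a Grade 3 or higher value in both arms, independently. The chance of at least one such value in k samples is 1 − (1 − p)^k.

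Hematology to week 24, k = 8 v 12 (loncastuximab tesirine first):

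- p = 1%: 1 − 0.99^8 = 7.7% v 1 − 0.99^12 = 11.4%
- p = 2%: 1 − 0.98^8 = 14.9% v 1 − 0.98^12 = 21.5%
- p = 5%: 1 − 0.95^8 = 33.7% v 1 − 0.95^12 = 46.0%

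Other chemistry to week 24 at p = 2%, k = 8 v 6: 14.9% v 1 − 0.98^6 = 11.4%. The sign reverses.

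As a rough guide to p, Section 1.2.3 reports Grade 3 or higher neutropenia of 16.9% for loncastuximab tesirine and 27% for idelalisib. These are adverse-event rates from other studies, but they make p = 5% look high.

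Independence is the generous case. If abnormal values persisted across all of a patient's samples, the two percentages would be equal. At p = 2% the hematology gap therefore lies between 0 and 21.5 − 14.9 = 6.6 points, depending on within-patient correlation.

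**4. Chance that a 7-day abnormality meets a scheduled sample.** Let it fall wholly within weeks 0 to 16 (days 0 to 112), with its start uniform over days 0 to 105. It is seen if it starts in the 7 days before a sample.

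- Loncastuximab tesirine: 5 such intervals, 5 × 7 / 105 = 33%
- Idelalisib hematology and ALT/AST/bilirubin: 7 intervals, 7 × 7 / 105 = 47%
- Idelalisib other chemistry: 3 intervals, 3 × 7 / 105 = 20%

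After week 28 the figures are 7/21 = 33% on loncastuximab tesirine and 7/28 = 25% on idelalisib for every analyte. The uniform start ignores any link to the infusion; an abnormality confined to mid-cycle would miss every scheduled pre-dose sample.

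**5. Weeks shared by both schedules to week 24**

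- Hematology: 6, 12, 18, 24
- ALT/AST/bilirubin: 6, 12, 24 (week 18 is lost because Day 15 liver tests stop after Cycle 4)
- Other chemistry: 12, 24

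**The case against.** **Safety analyses are descriptive (Section 9.8).** The safety objective concerns loncastuximab tesirine and words no comparison, no between-arm laboratory test is planned, and the Section 4.3 stopping rules use no laboratory grades. All of this stands and limits the consequence. It does not make the two columns comparable.

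**By-visit summaries are also planned.** They use scheduled data only, but by nominal visit. Cycle 5 Day 1 is week 12 on loncastuximab tesirine (4 × 3) and week 16 on idelalisib (4 × 4), so cycle labels do not line up.

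**Details are left to the SAP.** The SAP may address this, and its absence here proves no omission. But the all-sample rule is already stated in Section 9.8.2 and by itself gives percentages that depend on the schedule.

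Three stronger readings are tempting and are not supported:

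- *That the table overstates idelalisib toxicity in general.* A reader might infer this from the Day 15 tests. For GGT, ALP and other chemistry the frequency effect runs against loncastuximab tesirine, and GGT increase heads its Grade 3 or higher list in Section 1.2.3 at 21.3%.
- *That loncastuximab tesirine is sampled only pre-dose.* This holds for scheduled on-treatment samples. EOT and clinically indicated samples also enter the worst case, and holding doses until recovery under Table 4 implies rechecks.
- *That weekly idelalisib monitoring inflates Grade 3 or higher cytopenia.* Table 5 starts those tests at Grade 3, when the patient already counts for that parameter. They could reveal more Grade 4 values. For liver tests the trigger is Grade 2, so extra detection of Grade 3 is possible there.

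**Conclusion.** The point holds as an analyte- and time-specific comparability problem. The worst-case rule makes no allowance for schedules that differ by arm, so worst-grade percentages should not be read across arms. Frequency favors detection on idelalisib for hematology to week 28 and for ALT, AST and total bilirubin to week 16, with weekly liver tests from Grade 2 adding to it. It favors detection on loncastuximab tesirine for other chemistry throughout and for every analyte after week 28.

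The counts follow directly from Tables 1 and 2 on an undelayed schedule. The percentages are illustrations: they assume equal per-sample risk and independent samples, and the gap shrinks with correlation. No overall direction of bias can be claimed. Because safety is descriptive, this concerns interpretation and does not touch the trial's inference on efficacy. It is worth correcting because the remedy uses data already collected.

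**What to change.** In the SAP:

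1. Keep the all-sample worst-case table and label it a within-arm description.
2. Add a descriptive between-arm worst-grade table using one sample per patient per target week: weeks 6, 12, 18 and 24 for hematology; 6, 12 and 24 for ALT, AST and total bilirubin; 12 and 24 for other chemistry.
3. For each target week take the sample nearest in time within a prespecified window, whether scheduled or not. Do not take the worst value in the window. Loncastuximab tesirine samples follow dosing, so an exact-week grid would drop patients whose doses are delayed, including those delayed for toxicity; the nearest-sample rule is meant to retain them. Show how many patients contribute at each target week.
4. Report the number of samples per patient by arm and analyte.
5. Note in the table and the clinical study report that scheduled on-treatment loncastuximab tesirine samples are pre-dose and may miss mid-cycle changes. The matched table does not remove that limitation.

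The cost is SAP wording and one extra table that uses fewer samples. Monitoring and patient care do not change.

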9.8.3 Additional Safety Assessments

The results of scheduled assessments of vital signs, physical examinations, 12-lead ECGs and ECOG performance status will be summarized. All data will be reported according to the nominal visit date for which it was recorded (i.e., no visit windows will be applied). Unscheduled data will be included in “worst case” summaries, which will capture a worst case across all scheduled and unscheduled visits after the first dose of study treatment. All data will be listed. Further details will be provided in the SAP.

9.9 Pharmacokinetic and Pharmacodynamic Analyses

[figure not shown]
The PK profile will include, but is not limited to, determination of clearance and volume of distribution. As appropriate, other parameters of exposure may be derived at the patient level for cross-study comparisons [REDACTED]

PK parameters for the typical patient will be determined using a population PK analysis approach. A subset of relevant intrinsic and extrinsic covariate factors will be identified prior to analysis and assessed for their influence on drug disposition. As appropriate, PK data from prior loncastuximab tesirine studies may be leveraged to support the population PK model.

9.10 Immunogenicity Analyses

A tiered immunogenicity strategy (Figure 3) will be undertaken to evaluate ADAs by screening and confirmatory assays with titer evaluation, followed by characterization and evaluation of neutralizing capacity as needed. ADA sample collection, banking, and testing in validated and to be validated assays will be according to [FDA Immunogenicity Testing of Therapeutic Protein Products —Developing and Validating Assays for Anti-Drug Antibody Detection Guidance for Industry \(Jan 2019\)](#).

Figure 3. Anti-drug Antibody Tiered Immunogenicity Testing Strategy

Abbreviations: ADA=anti-drug antibody; ADC=antibody-drug conjugate; BSA=bovine serum albumin; mAb=monoclonal antibody; PK=pharmacokinetics.

Results from ADA testing will include tabular summarization for number/proportion of patients with positive pre-dose ADA response, number of patients with post dose ADA response only, and number of patients with positive ADA response at any time. The denominator will be the total number of patients tested for ADAs in the study. For patients exhibiting a positive ADA, PK, safety and efficacy correlates will be assessed and reported.

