7.5.1 Pharmacokinetics

The concentration in serum of loncastuximab tesirine (total antibody), PBD-conjugated antibody, and unconjugated warhead SG3199 for samples taken prior to and immediately after dosing on Cycles 1 through 6, and end of treatment in patients on loncastuximab tesirine will be assessed by a central laboratory designated by the Sponsor using validated bioanalytical methods. In addition, matching PK samples will be drawn at ADA collection time points from Cycle 7 and beyond during study treatment.

Approximately 6 mL of whole blood will be collected as per [Table 1](#) and [Table 6](#). Blood should be drawn from a vein away from the one used for study drug infusion.

PK samples must be stored at $\leq -70^{\circ}\text{C}$. Please refer to the laboratory manual for detailed instructions regarding specimen handling and shipment.

At timepoints coinciding with ECG collection, PK blood collection should occur immediately after the end of the ECG recording and, when applicable, after vital signs.

To understand the metabolic disposition of loncastuximab tesirine in humans, samples remaining after PK analysis is complete may be pooled among patients for potential metabolite identification.

Table 6. Sampling Schedule for ECG, PK, ADA and [REDACTED]

Cycle	Day	ECG timepoint	PK timepoint loncastuximab tesirine arm only	ADA timepoint loncastuximab tesirine arm only	[REDACTED]
Screening	-28 to -1	X			
C1-C6	D1	C1: Pre-dose only C2: Pre-dose for all subjects & EOI (Within 10 min prior to EOI) for loncastuximab tesirine arm only	X Pre-dose & EOI: Within 10 min post EOI	C1, C3, and C5 only: Pre-dose	
C7 & Beyond	D1		C7, then every other cycle Pre-dose	C7, then every other cycle Pre-dose	
EOT		Anytime during EOT visit	X	X	
Follow-Up				If ADA positive is detected, additional ADA samples may be requested for testing every 12 weeks until the ADA titer falls to the baseline level	

**Pre-dose: preferably within 2 h prior to start of infusion

Abbreviations: ADA=anti-drug antibody; C=cycle; D=day; ECG=electrocardiogram; EOI=end of infusion; EOT=end-of-treatment; h=hour; min=minute; PK=pharmacokinetics; [REDACTED]; IP=Investigational Product

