7.5.2 Immunogenicity

Detection of ADAs will be performed by using a screening assay for identification of antibody-positive samples/patients, a confirmation assay, and titer assessment and will be performed using the Meso-Scale Discovery Electrochemiluminescence platform. If an ADA is confirmed, a functional assay for the assessment of the neutralizing capacity of the ADA will be performed.

Blood samples for ADA testing will be collected pre-dose on C1D1, then Day 1 of every other cycles from patients assigned to loncastuximab tesirine arm only. Up to 6 mL of whole blood will be collected each time as per [Table 1](#) and [Table 6](#).

Blood should be drawn from a vein away from the one used for study drug infusion.

For patients who test positive for ADA, additional ADA samples may be requested for testing every 12 weeks following the EOT visit until the ADA titer falls to the baseline level

ADA samples must be stored at $\leq -70^{\circ}\text{C}$. Please refer to the laboratory manual for detailed instructions regarding specimen handling and shipment.

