9.1 Sample Size Determination

Approximately 150 patients will be enrolled and randomly assigned to treatment with loncastuximab tesirine or idelalisib in a 2:1 ratio. The study is over-powered for the primary efficacy endpoint when a 55% of CRR in loncastuximab tesirine (compared to observed 64.3% CRR in Phase 1 trial) and 15% from idelalisib ([Salles G, 2017](#)) are assumed. The purpose of a larger sample size and 2:1 randomization ratio is to provide a more robust safety data set (~100 FL patients treated with loncastuximab tesirine). [Table 8](#) and [Table 9](#) summarizes the study power when different CRR and ORR are expected.

Table 8. Power for Primary Endpoint CRR with 2-Sided Significance Level 0.05

Expected CRR from loncastuximab tesirine arm*	55%	45%	40%
CRR from idelalisib arm**	15%	15%	15%
Power***	99%	96.1%	87.3

* Data from Phase 1 trial (ADCT-402-101) shows that CRR is approximately 64%, lower CRRs are assumed in this study

** CRR from idelalisib is assumed to be 15% ([Salles G, 2017](#))

*** Based on nquery fisher's exact test

Table 9. Power for Key Secondary Endpoint ORR with 2-Sided Significance Level 0.05

Expected ORR from loncastuximab tesirine arm*	79%	75%	70%
ORR from idelalisib arm**	54%	54%	54%
Power***	84.1%	67.3%	41.7%

* Data from Phase 1 trial (ADCT-402-101) shows that ORR is approximately 79%.

**ORR from idelalisib is assumed to be 54% ([Idelalisib® US- Prescribing Information](#)).

*** Based on nquery fisher's exact test

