9.2 Analysis Populations

- Intent-to-treat (ITT) Population: All patients who are randomized. This population will be used in the primary analyses of efficacy.
- All-Treated Population: All patients who receive at least 1 dose of loncastuximab tesirine or idelalisib. This population will be used in the primary analyses of safety.
- Per-Protocol Population: All patients in the all-treated population without important protocol deviations, which will be further described in detail in the SAP.
- The PK Population: All patients who receive loncastuximab tesirine and have at least 1 pre-(C1D1) and 1 post dose valid assessment.
- The Immunogenicity Population: All patients who receive loncastuximab tesirine and have at least 1 valid ADA assessment.
- The Pharmacodynamic Population: All patients who receive study drug and have at least 1 valid pharmacodynamics/ [REDACTED]
- Patient-reported Outcomes Population: All patients who receive at least 1 dose of study treatment and complete at least one questionnaire at baseline and at one postbaseline visit.

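### Section 9.10 divides all ADA rows by everyone ever tested, so patients with only a pre-dose sample can pull the post-dose and any-time proportions down

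*Combined protocol and SAP*

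**What the plan says.** Section 9.10 plans three tabulated ADA summaries: patients positive before dosing, the "number of patients with post dose ADA response only", and patients positive at any time. One sentence on the denominator follows the list: "The denominator will be the total number of patients tested for ADAs in the study". It is not limited to any row.

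Section 9.2 defines the Immunogenicity Population as "All patients who receive loncastuximab tesirine and have at least 1 valid ADA assessment". No post-dose result is required. The PK Population in the same list is stricter: "All patients who receive loncastuximab tesirine and have at least 1 pre-(C1D1) and 1 post dose valid assessment".

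On timing, Section 7.5.2 says "Blood samples for ADA testing will be collected pre-dose on C1D1, then Day 1 of every other cycles". Table 6 (Section 7.5.1) gives the early time points as "C1, C3, and C5 only: Pre-dose", then Cycle 7 and every other cycle. Tables 1 and 6 also mark an ADA sample at the end-of-treatment (EOT) visit. With 3-week cycles, the first scheduled on-treatment sample after exposure is at about week 6.

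**The concern.** A patient enters the denominator at the first blood draw, before any drug has been given. To enter the post-dose numerator, the same patient needs a later sample. Someone who leaves before Cycle 3 without an EOT sample is therefore handled as if tested after exposure and found negative, when no such test was done.

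Evaluating immunogenicity is a stated secondary objective, and Section 9.10 is the only ADA summary plan in the text. A proportion that counts untested patients as negative makes the drug look somewhat less immunogenic than the data show, and a table giving one N would not reveal it. The PK Population shows that the plan already uses a pre-dose and post-dose evaluability rule elsewhere.

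**Working it through.** The documents state no ADA incidence, ADA sample size or ADA precision, so there is no planned figure to reproduce. The check is algebraic, with assumed inputs marked.

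**Inputs**
- N, patients tested: about 100, from the planned "100 FL patients treated with loncastuximab tesirine" (Section 9.1).
- k, treated patients with a pre-dose sample and no post-dose sample: not given. Assumed 0 to 15 of 100.
- Post-dose rate among patients with a post-dose result: not given. Assumed 10%.

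**Post-dose-only row.** Let x be the number positive only after dosing. All x come from the N − k patients with a post-dose result.
- Reported rate = x/N.
- Rate among patients with a post-dose result = x/(N − k).
- Ratio = (N − k)/N, which cannot exceed 1.

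| k of 100 (assumed) | Factor | Reported rate if the evaluable rate is 10% (assumed) | Evaluable rate if 10 positives are seen (assumed), reported as 10.00% |
|---|---|---|---|
| 0 | 1.00 | 10.0% | 10.00% |
| 5 | 0.95 | 10% × 0.95 = 9.5% | 10/95 = 10.53% |
| 10 | 0.90 | 10% × 0.90 = 9.0% | 10/90 = 11.11% |
| 15 | 0.85 | 10% × 0.85 = 8.5% | 10/85 = 11.76% |

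**Any-time row.** Patients with no post-dose sample had no chance of a later positive, so the count can only be at or below what full sampling would have given. The exact factor (N − k)/N applies here if none of the k patients was positive before dosing. If some were, they count as any-time positive. The shortfall against evaluable patients is then smaller and could reverse, although the shortfall against full sampling remains.

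**Pre-dose row.** This row is not affected by missing post-dose samples.

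**How likely is k above zero?** If each of 100 patients independently lacks a post-dose sample with probability q (assumed), the chance of at least one is 1 − (1 − q)^100. That is 63% at q = 1%, 87% at 2%, 95% at 3% and 99% at 5%.

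**A second leak in the post-dose-only row.** Patients positive before dosing cannot be positive only after dosing, yet they stay in the denominator. Assume 5 post-dose-only positives, k = 5, and 3 pre-dose positives who do have post-dose samples. The plan then reports 5/100 = 5.00%, against 5/(100 − 5 − 3) = 5/92 = 5.43% among patients at risk.

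**The case against.** A reader might infer that immunogenicity is understated by construction. The documents do not support that. A patient who stops before Cycle 3 is still scheduled for an ADA sample at EOT (Tables 1 and 6), and Section 5.5.1 asks patients who stop treatment to attend that visit. Only patients who die, withdraw or are lost early with no EOT sample are affected. If there are none, the effect is zero. This stands and limits the point, but it does not guarantee k = 0. Section 5.5.2 ends data collection when consent is withdrawn, and Section 5.5.1 allows status to be obtained by phone, email or mail, which yields no blood sample.

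A reader might also infer that a named secondary endpoint is biased. The endpoint in Table 3 is ADA titers, which do not depend on this denominator. What is affected is a descriptive incidence summary with no hypothesis test.

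Three further objections have weight:
- Section 9.10 mentions a proportion explicitly only for the pre-dose row, so the denominator might be meant for that row alone. The sentence follows all three rows, which makes a shared denominator the likelier reading. If the narrow reading is intended, the text should say so.
- The shift is small beside sampling error. The exact 95% interval for 10 of 100 is roughly 5% to 18%, and the assumed shift is at most 1.5 percentage points. The shift has one direction, however, and can be avoided without cost to the trial.
- Section 9 defers full detail to a SAP. That would answer an omission, but Section 9.10 states its denominator without qualification, and nothing in the text replaces it.

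Finally, changing the denominator does not recover the ADA rate in patients who left early. It only stops counting them as negative, which is why their number should be shown.

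**Conclusion.** The point holds in a limited form. On the likelier reading of Section 9.10, treated patients without a post-dose sample count as not post-dose positive. The post-dose-only proportion is then understated by the factor (N − k)/N, and the any-time proportion can only fall short of what full sampling would show.

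The size is unknown and probably modest. With k assumed at 0 to 15 of about 100 and an assumed 10% rate among evaluable patients, the reported rate is 10% to 8.5%. Neither k nor the rate is given in the documents, and zero effect is within the range. ADA titers, the complete response rate and the overall response rate are untouched. It is a stated rule that can err in one direction, and it is worth correcting because the correction is cheap.

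**What to change.** In Section 9.10 and the SAP, replace the single denominator with one for each row:
- **Pre-dose positivity:** patients with a valid pre-dose sample.
- **Post-dose-only positivity:** patients with a valid negative baseline and at least one valid post-dose result.
- **Any-time positivity:** patients with at least one valid post-dose result, with the numerator counted in the same patients.

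Print each denominator in the table and report the number of treated patients with no post-dose sample.

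The cost is wording and table shells; no extra samples, visits or patients are needed. The downside is that the reported incidence may be slightly less favourable and rest on slightly fewer patients.
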